9.6 Efficacy Subgroup Analyses

To evaluate the consistency of the efficacy over demographic and other baseline disease characteristics, the primary efficacy endpoint will be analyzed in selected subgroups as follows:

- Age group (< 40 years, ≥ 40)
- Sex (male, female)
- Race (white, non-white)

- Smoking (current, ex- or never)
- Body mass index (BMI) (normal: < 25, overweight: ≥ 25 to < 30, obese: ≥ 30)
- Baseline ppIGA ("moderate" [3], "severe" [4])
- Baseline BSA (< 10% versus ≥ 10%);
- Psoriatic arthritis (yes, no)
- Body weight (≤ 100 kg, > 100 kg)

Of note, if the BMI ≥ 30 subgroup have fewer than 10% of the total subjects, it will be combined with its adjacent subgroup.

10.0 Safety Analyses

10.1 General Considerations

Safety analyses will include adverse events, laboratory, and vital sign measurements.

Safety data will be summarized among the Safety_A and Safety_B populations by treatment groups. For the safety analysis, subjects are analyzed based on the actual treatment group, determined by the first dose of study drug that the subject received.

The overview of TEAEs, areas of safety interest (ASIs), and potentially clinically important (PCI) findings in laboratory variables and vital sign variables will be summarized among the ALL_RZB Population.

Missing safety data will not be imputed.

10.2 Adverse Events

Adverse events (AEs) will be summarized and presented using primary MedDRA System Organ Classes (SOCs) and preferred terms (PTs) according to the version of the MedDRA coding dictionary used for the study at the time of database lock. The actual version of the MedDRA coding dictionary used will be noted in the AE tables and in the clinical study report. When summarizing the number and percentages of subjects, subjects with

multiple occurrences of the same adverse event will be counted once, and only the maximum severity level will be presented in the severity summaries, and the worst/highest relationship level in the relationship summaries.

10.2.1 Treatment-Emergent Adverse Events

Treatment-emergent adverse events (TEAEs) for each safety period are defined as follows:

Period A: A TEAE in Period A is defined as any event with an onset date on or after the first dose date of study drug in Period A and within 140 days after the last dose date of study drug in Period A, as long as it does not exceed the first dose date in Period B.

Period B: A TEAE in Period B is defined as any event with an onset date on or after the first dose date of study drug in Period B and within the minimum of (140 days after the last dose date of study drug in Period B, and the end of study date).

The All-Risankizumab Treated Period: A TEAE is defined as any event with an onset date on or after the first dose date of risankizumab and within the minimum of (140 days after the last dose date of risankizumab, and the end of study date).

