5.3 Prohibited Medications and Therapy

- 1. During the study, no biologic treatment is allowed. Exception: Treatment with commercially available risankizumab after the Week 52/Premature Discontinuation (PD) assessments if this has been determined as an appropriate subsequent treatment by the investigator in discussion with the subject.
- 2. Systemic (including oral or injectable administrations) non-biologic therapy that can be used to treat PsO, including but not limited to cyclosporine, corticosteroids, methotrexate, retinoids, apremilast, and fumaric acid derivatives.
- 3. Phototherapy treatment (UVB or ultraviolet A [UVA] phototherapy, including PUVA), laser therapy, tanning booth, or extended sun exposure that could affect disease severity or interfere with disease assessments.
- 4. Topical PsO treatments, including but not limited to corticosteroids, anthralin, calcipotriene, topical vitamin D derivatives, retinoids, urea, α- or β-hydroxyl acids, and medicated shampoos (for example those that contain corticosteroids, coal tar, or vitamin D3 analogues).
- 5. All other investigational drugs and enrollment in another clinical study are prohibited.
- 6. Live attenuated vaccines are not permitted during study participation and including up to 140 days (20 weeks or as guided by the local risankizumab label [if approved], whichever is longer) after the last dose of study drug. Examples of live attenuated vaccines include, but are not limited to, the following:
 - Bacille Calmette-Guérin (BCG)
 - Zoster vaccine live (Zostavax[®])
 - Measles mumps rubella or measles mumps rubella varicella
 - Monovalent live attenuated influenza A (intranasal)
 - Oral polio vaccine
 - Rotavirus
 - Seasonal trivalent live attenuated influenza (intranasal)
 - Smallpox
 - Oral typhoid vaccine

- Varicella (chicken pox)
- Yellow fever
- Dengue (Dengvaxia[®])

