Important Medical Event Requiring Medical or Surgical Intervention to Prevent Serious Outcome An important medical event that may not be immediately life-threatening or result in death or hospitalization, but based on medical judgment may jeopardize the subject and may require medical or surgical intervention to prevent any of the outcomes listed above (i.e., death of subject, life-threatening, hospitalization, prolongation of hospitalization, congenital anomaly, or persistent or significant disability/incapacity). Additionally, any elective or spontaneous abortion or stillbirth is considered an important medical event, along with any suspected transmission of an infectious agent via a medicinal product if no other serious criterion is applicable. Examples of such events include allergic bronchospasm requiring intensive treatment in an emergency room or at home, blood dyscrasias or convulsions that do not result in inpatient hospitalization, or the development of drug dependency or drug abuse.

All AEs reported from the time of study drug administration until 140 days (20 weeks) after discontinuation of study drug administration will be collected, whether solicited or spontaneously reported by the subject. In addition, study procedure-related serious and nonserious AEs will be collected from the time the subject signs the study-specific informed consent.

The following definitions will be used for Serious Adverse Reaction (SAR) and Suspected Unexpected Serious Adverse Reaction (SUSAR):

- SAR Defined as all noxious and unintended responses to an Investigational Medicinal Product (IMP) related to any dose administered that result in an SAE as defined above.
- SUSARRefers to individual SAE case reports from clinical trials where a causal
relationship between the SAE and the IMP was suspected by either the sponsor
or the investigator, is not listed in the applicable Reference Safety Information
(RSI), and meets one of the above serious criteria. All individually reported SARs
are considered suspected.

AbbVie will be responsible for SUSAR reporting for the IMP in accordance with global and local requirements.

Adverse events will be monitored throughout the study to identify any of special interest that may indicate a trend or risk to subjects.

Areas of Safety Interest/Safety Topics of Interest

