10.2.4 Treatment-Emergent Adverse Events per Patient-Years of Exposure

Exposure-adjusted TEAEs per 100 patient-years will be provided, where TEAEs per 100 patient-years of exposure are defined as the number of TEAEs divided by the total exposure in 100 patient-years.

Note that one event per preferred term per day per subject will be counted in the calculation of the number of TEAEs (i.e., a preferred term will not be counted twice on

the same day for the same subject). The exposure-adjusted TEAE rate per 100 patient-years is calculated as:

$$100 \times \frac{\text{Number of TEAEs}}{\text{Total Patient Years}}$$

where total patient years in each period are defined below.

Total patient years in Period A: Sum of study drug exposure in Period A, defined as the minimum of (the last dose date in Period A + 140 days, the end of study date + 1 day, and the first dose date in Period B if not missing [and the cutoff date during the Primary Analysis + 1 day]) minus the first dose date in Period A, normalized by 365.25 and rounded to one decimal place.

Total patient years in Period B: Sum of study drug exposure in Period B, defined as the minimum of (the last dose date in Period B + 140 days, and the end of study date + 1 day [and the cutoff date during the Primary Analysis + 1 day]) minus the first dose date in Period B, normalized by 365.25 and rounded to one decimal place.

Total patient years in the All-Risankizumab Treated Period: Sum of study drug of risankizumab exposure, defined as the minimum of (the last risankizumab dose date + 140 days, and the end of study date + 1 day [and the cutoff date during the Primary Analysis + 1 day]) minus the first risankizumab dose date, normalized by 365.25 and rounded to one decimal place.

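### The Period A TEAE window has no end-of-study limit but its patient-year denominator does, so events recorded after study exit enter the per-100-PY rate without exposure time

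*SAP*

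**What the plan says.** SAP 10.2.1 gives three TEAE windows:

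- **Period A:** onset from the first dose and "within 140 days after the last dose date of study drug in Period A, as long as it does not exceed" the first dose in Period B. There is no end-of-study term.
- **Period B:** onset from the first Period B dose and "within the minimum of (140 days after the last dose date of study drug in Period B, and the end of study date".
- **ALL_RZB:** onset from the first risankizumab dose and "within the minimum of (140 days after the last dose date of risankizumab, and the end of study date".

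SAP 10.2.4 builds Period A patient-years from "the minimum of (the last dose date in Period A + 140 days, the end of study date + 1 day" and the first Period B dose if there is one (plus a data-cutoff term at the Primary Analysis), less the first dose date. The Period A denominator therefore does stop at the end of study.

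Four other provisions bear on this:

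- Protocol 6.1 has AEs "until 140 days (20 weeks) after discontinuation of study drug administration will be collected".
- Protocol 5.6 keeps subjects who stop only study drug in scheduled follow-up. It offers those who leave the study an optional call at 140 days, and does not require that call of anyone who starts commercial risankizumab.
- Protocol 5.3 permits "Treatment with commercially available risankizumab after the Week 52/Premature Discontinuation (PD) assessments".
- SAP 10.1 groups subjects for safety by the treatment first received.

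Neither document defines an end of study date for the individual subject. Protocol Section 11 defines it for the trial as a whole.

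**The concern.** A per-100-PY rate is interpretable only if events and exposure are counted over the same time. The SAP keeps them matched in Period B and in ALL_RZB but not in Period A, which is the only placebo-controlled safety comparison. No reason is given for the difference, and it reads as an omission.

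The rate rises with the number of subjects who leave the study early, whatever the drug does. An arm contributes only about 25 patient-years in Period A, so one event without exposure moves its rate by about 100/25 = 4 per 100 PY. That matters most for infrequent events: Protocol 7.5 plans such rates for SAEs, deaths and AEs leading to discontinuation.

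**Working it through.** The plan states no figure for this quantity, so there is none to reproduce. The check is day arithmetic on the two definitions.

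**Inputs from the documents.** First dose Day 1; second Period A dose Day 29 (Week 4); Week 16 visit and first Period B dose Day 113 (Protocol Appendix D); 84 subjects per arm (SAP 2.4).

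**Assumed inputs.** The number and timing of study exits; a constant event rate; full reporting after exit; end of study date equal to exit date.

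**Formulas, no data cutoff.**
- Last event-eligible day = min(last Period A dose + 140, first Period B dose if any).
- Exposure days = min(last Period A dose + 140, exit day + 1, first Period B dose if any) − 1.
- Uncovered days = last event-eligible day − exit day, if positive.

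**Subject who enters Period B on Day 113.** The window ends on Day 113. Exposure is min(169, 113) − 1 = 112 days. There is no material mismatch.

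**Subjects who leave the study with no Period B dose.**

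| Last dose | Exit | Last eligible day | Exposure days | Uncovered days |
|---|---|---|---|---|
| Day 29 | Day 29 | 169 | 29 | 140 |
| Day 29 | Day 57 | 169 | 57 | 112 |
| Day 29 | Day 85 | 169 | 85 | 84 |
| Day 29 | Day 113 | 169 | 113 | 56 |
| Day 29 | Day 169 | 169 | 168 | 0 |
| Day 1 | Day 15 | 141 | 15 | 126 |
| Day 1 | Day 29 | 141 | 29 | 112 |
| Day 1 | Day 57 | 141 | 57 | 84 |

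**Arm level.** Let k of 84 subjects leave on Day 57 after a Day 29 dose, and let the rest enter Period B. At a constant event rate the rate itself cancels, and the maximum relative inflation is

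112k / [(84 − k) × 112 + 57k].

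- k = 3: 336 / (9,072 + 171) = 336 / 9,243 = 3.6% (25.3 PY counted)
- k = 6: 672 / (8,736 + 342) = 672 / 9,078 = 7.4% (24.9 PY)
- k = 8: 896 / (8,512 + 456) = 896 / 8,968 = 10.0% (24.6 PY)

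**Sensitivity to exit day.** Replace 57 by the exit day, and the 112 in the numerator by 169 − exit day. For k = 8, exit on Day 36 gives 1,064 / 8,800 = 12.1%, and exit on Day 85 gives 672 / 9,192 = 7.3%. For k = 3, the same two days give 399 / 9,180 = 4.3% and 252 / 9,327 = 2.7%.

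**Sensitivity to reporting.** The inflation scales with the share of post-exit events that are recorded. At one half, the Day 57 figures fall to 1.8%, 3.7% and 5.0%.

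**Between arms.** Equal exits in both arms (say 6 and 6) inflate both rates by 7.4% and leave the rate ratio unchanged. Exits of 8 against 3 would shift the ratio by at most 1.100 / 1.036 = 1.06, in a direction set by which arm has the 8.

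**With the window capped at the end of study date.** For exit on Day 57, eligible days and exposure days are both 57. For exit on Day 85 both are 85. Uncovered days are 0 in every exit scenario.

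**The case against.** The strongest defence is that the gap depends on an undefined date. If a subject's end of study date is the last contact, including the 140-day call, exposure runs to that call and the gap nearly closes. That is correct. It also means that, as written, the rate depends on a programming choice the SAP does not make.

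The Period A window also agrees with Protocol 7.5, which sets 140 days after the last dose with no end-of-study limit, and with the collection period in Protocol 6.1. A cap therefore takes some protocol-defined TEAEs out of the Period A tables. This stands as a cost, and is why the later events should be listed. Extending the denominator to 140 days would also reconcile the two definitions, but it would credit time in which the plan requires no contact with the subject.

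Several stronger readings are tempting, and the documents do not support them:

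- **That everyone who stops treatment in Period A is affected.** Subjects who stop only study drug stay in follow-up under Protocol 5.6, and their exposure continues to accrue.
- **That all Period A safety tables are mismatched.** The overview and SOC/PT tables count subjects and use no patient-years. They can include the same late events, but have no such denominator.
- **That events count against the randomised arm.** Safety is grouped by actual treatment.
- **That the bias favours risankizumab because placebo subjects leave and start the commercial product.** The wording allows such an event to be tabulated under placebo, and a placebo leaver is not in ALL_RZB, which requires risankizumab as study drug. But Protocol 5.6 waives the 140-day call for these subjects, so such events would come mainly from spontaneous reports. Nothing in the documents says which arm will have more exits.

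**Conclusion.** The inconsistency is real and confined. In Period A the event window can run past the exposure time, whereas the SAP's own rule for the other two safety periods prevents this. It affects only the Period A per-100-PY rates, and only through subjects who leave the study within 140 days of their last Period A dose without a Period B dose.

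The figures of about 4%, 7% and 10% are upper bounds for one arm. They rest on assumed exits (3, 6 or 8 of 84, all on Day 57), a constant event rate, full reporting after exit, and an end of study date equal to the exit date. Incomplete reporting lowers them, and a last-contact definition brings them close to nil. The direction of any between-arm bias is unknown. Efficacy, power and type I error are unaffected. The change is worth making because it costs little and removes an avoidable ambiguity from the only controlled safety comparison.

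**What to change.** - In SAP 10.2.1, end the Period A window at the earlier of 140 days after the last Period A dose and the end of study date, still cut at the first Period B dose.
- Define the subject-level end of study date once in the SAP, stating whether it is the exit visit or the last contact including the 140-day call. Use that definition in both 10.2.1 and 10.2.4.
- List events with onset after that date separately, including any known to follow the start of commercial risankizumab, so that none is lost.

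A cut-off at the start of commercial risankizumab in all three safety periods is not proposed. It goes beyond the inconsistency shown, and it needs a date that no required contact collects once the 140-day call is waived.

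The cost is a few lines of SAP text. The downside is that a few late events move from the Period A tables to a listing.

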Randomization/drug assignment		✓						
Study drug administration		×	×	×	✓	×		
Dispense urine pregnancy tests for women of child-bearing potential (for potential virtual visits due to COVID-19)		~						

Activity	Screening	Baseline	Week 4	Week 16	Week 28	Week 40	Week 52/Premature Discontinuation	
			Day 29	Day 113	Day 197	Day 281	Day 365	20 Week Safety
Visit window	Day -35 to -1	Day 1	± 3	days		± 7 da	ys	F/U Call
Dispense Subject Dosing Diary (for potential virtual visits due to COVID-19)		~						
Self-Injection Training		×		✓				
Hypersensitivity Training		 Image: A second s		×				
Hypersensitivity monitoring		✓	~	✓	~	✓		

BL = Baseline; BSA = Body surface area; CBC = Complete blood count; COVID-19 = coronavirus disease – 2019; DLQI = Dermatology Life Quality Index; ECG = Electrocardiogram; FSH = Follicle-stimulating hormone; F/U = Follow-up; HBV = Hepatitis B virus; HCV = Hepatitis C virus; HIV = Human immunodeficiency virus; IGRA = Interferon gamma release assay; PASI = Psoriasis Area and Severity Index; PD = Premature Discontinuation; PGA-SP = Patient Global Assessment of Skin Pain; PPD = Purified protein derivative; PPASI = Palmoplantar Psoriasis Area and Severity Index; ppIGA = Palmoplantar Investigator's Global Assessment; PSS = Psoriatic Symptom Scale; SARS-CoV-2 = Severe acute respiratory syndrome coronavirus 2; sPGA = static Physician's Global Assessment; TB = Tuberculosis

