2.2 Study Design Overview

This is a Phase 3b, multicenter, randomized, double-blind, parallel group, placebo-controlled study to evaluate the safety and efficacy of risankizumab (150 mg) compared to placebo in adult subjects with moderate to severe plaque psoriasis with palmoplantar involvement.

The study is comprised of a Screening period of up to 35 days, a 52-week treatment period, and a follow up phone call for safety.

[figure not shown]
The 52-week treatment period includes Period A and Period B.

- Period A, Double-Blind Period (Baseline to Week 16): Eligible subjects will be centrally randomized at the Baseline visit in a 1:1 ratio to receive either risankizumab 150 mg as a single subcutaneous (SC) injection, or matching placebo. Study drug administration will occur at Baseline and Week 4. The final efficacy evaluation of Period A will be at Week 16.
- Period B, Open-Label Period (Week 16 to Week 52): Starting at Week 16, all subjects will receive open label risankizumab 150 mg once every 12 weeks at Weeks 16, 28, and 40. The final efficacy evaluation of Period B will take place at Week 52.

A follow-up phone call for safety will be conducted approximately 20 weeks after administration of the last dose of risankizumab (e.g., Week 60).

The schematic of the study is shown in [Figure 1](#).

Figure 1. Study Schematic

Solid arrows indicate administration of study drug at study visits.

Wk = week.

The Primary Analysis will be performed after the last ongoing subject completing the Week 16 visit or permanently discontinuing the placebo-controlled period, and the data up to Week 16 cutoff date have been cleaned.

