9.0 Efficacy Analyses

9.1 General Considerations

All efficacy analyses will be conducted among the ITT Population. All statistical tests will be performed at a 2-sided alpha level of 0.05.

The Primary Analysis will be conducted after all continuing subjects complete Week 16 and all data pertaining to Period A are cleaned. This will be the only and final analysis for efficacy in Period A. Study sites and subjects will remain blinded to their initial treatment assignment for the duration of the entire study.

For categorical endpoints, comparisons will be made between risankizumab and placebo using the Cochran-Mantel-Haenszel (CMH) test, adjusting for the actual values of stratification factors (Baseline ppIGA and Baseline BSA categories). In case of any stratum with zero subject in either treatment group, no stratification factor will be controlled. Non-responder imputation (NRI) incorporating multiple imputation (MI) to handle missing data due to COVID-19 (NRI-C) will be the primary approach to handle missing values.

For continuous endpoints, comparisons will be made between risankizumab and placebo based on the fixed term of treatment from a Mixed-effect Model Repeat Measurement (MMRM) model including the Baseline value and observed measurements at all post-baseline visits, adjusting for the fixed effects of treatment, actual values of stratification factors, visit and treatment-by-visit interaction as covariates. The MMRM will be the primary approach to handle missing values.

"Baseline" refers to the last non-missing observation on or before the date of the first administration of study drug or the date of randomization if no study drug is administered. For variables where the assessment time is collected on the ePRO device, the baseline measurement must be prior to the time of the first administration of study drug.

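### SAP 10.2.1 counts an event starting on the first Period B dose date in both periods, so a placebo subject's same-day reaction to a first risankizumab injection is reported under placebo

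*SAP*

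**What the plan says.** SAP 10.2.1 defines treatment-emergent events separately for each period, by onset date. Period A runs from the first Period A dose date to 140 days after the last Period A dose, with the onset allowed "as long as it does not exceed the first dose date in Period B". Period B takes "any event with an onset date on or after the first dose date of study drug in Period B", up to its own 140-day and end-of-study limits.

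SAP 10.2.4 computes Period A exposure as the earliest of several dates minus the first Period A dose date. Those dates include "the end of study date + 1 day, and the first dose date in Period B if not missing". One day is added to the end-of-study date (and to the cutoff date at the Primary Analysis) but not to the first Period B dose date. In the event rate, "one event per preferred term per day per subject will be counted".

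On grouping, SAP 10.1 states that "subjects are analyzed based on the actual treatment group, determined by the first dose of study drug that the subject received". On treatment, SAP 2.2 states: "Starting at Week 16, all subjects will receive open label risankizumab 150 mg once every 12 weeks". Protocol 7.5 defines treatment-emergent events for the study as a whole and sets no boundary between the periods.

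**The concern.** The Period A upper bound and the Period B lower bound both include the first Period B dose date. For a subject randomised to placebo, that is the date of the first risankizumab injection. A reaction within hours of the injection cannot be an effect of that injection under placebo, yet it enters the placebo column of the Period A tables because the treatment label is fixed by the first dose received. The risankizumab arm's Period A column likewise gains events from its own Week 16 dosing day, although there the drug label is right.

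Period A is the only randomised safety comparison in the trial. The events most exposed are those that start on a dosing day, and SAP Appendix B lists injection site reactions, hypersensitivity and adjudicated anaphylactic reactions as areas of safety interest. The Protocol Appendix D schedule includes "Hypersensitivity monitoring" at Week 16, so same-day reactions are actively looked for at that visit.

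**Working it through.** The plan states no figure on this point to reproduce. The check is one of date logic, followed by the size of the effect.

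**1. Is the overlap real?** Let A1 and B1 be the first dose dates in Periods A and B, and LA the last Period A dose date.

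- Period A event: onset ≥ A1, onset ≤ LA + 140, onset ≤ B1.
- Period B event: onset ≥ B1 (upper limits not relevant here).

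These rules were applied with LA on Day 1, 26, 29 or 32 and B1 on Day 110, 113 or 116, which gives 12 combinations. In every one:

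| Onset | Period A | Period B |
|---|---|---|
| B1 − 1 day | yes | no |
| B1 | yes | yes |
| B1 + 1 day | no | yes |

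The overlap is exactly one calendar day. The 140-day limit does not remove it: a last dose on Day 29 gives Day 169, and a subject dosed only on Day 1 still reaches Day 141. Both fall after Day 113.

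**2. Events against exposure.** On the nominal schedule (Protocol Appendix D: Week 16 = Day 113), Period A events can start on Days 1 to 113, which is 113 days. SAP 10.2.4 gives 113 − 1 = 112 days of Period A exposure, and Period B exposure begins at B1. The switch day is in the Period A numerator but not in its denominator, a mismatch of 1/112 = 0.9%. With a strict bound (onset < B1) the event window is Days 1 to 112, and the two agree.

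**3. What one misplaced event is worth.** Take 84 placebo subjects (SAP 2.4), all assumed to enter Period B on schedule.

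- Exposure: 84 × 112 / 365.25 = 25.76 patient-years.
- Rate per event: 100 / 25.76 = 3.88 per 100 patient-years.
- Subjects: 1/84 = 1.19%. This is an upper figure, because a subject already counted for that event adds nothing.

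**4. Dosing-day events, as an illustration.** Assume all three doses (Weeks 0, 4 and 16) are given and that the same-day event rate per injection is constant within drug, pR for risankizumab and pP for placebo. Write R = pR/pP.

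- Strict window, events per subject: 2pR against 2pP. Ratio R, difference 2(pR − pP).
- SAP window: 3pR against 2pP + pR. Ratio 3R/(2 + R), difference again 2(pR − pP).

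| True R | Ratio under the SAP window |
|---|---|
| 2 | 6/4 = 1.50 |
| 3 | 9/5 = 1.80 |
| 5 | 15/7 = 2.14 |
| 10 | 30/12 = 2.50 |

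The reported ratio cannot exceed 3, however large R is. The absolute difference is unchanged.

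**5. If the risankizumab rate varies by injection.** Let p1, p2 and p3 be the same-day rates at the first, second and third risankizumab injections. The strict difference is p1 + p2 − 2pP. The SAP difference is (p1 + p2 + p3) − (2pP + p1) = p2 + p3 − 2pP. The bias is p3 − p1. Each 0.01 of gap equals 0.84 events in 84 subjects, or 100 × 0.84 / 25.76 = 3.26 per 100 patient-years. The documents do not give p1 or p3, so neither the sign nor the size of this bias is known.

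**The case against.** The wording does overlap; the best defence is that little follows from it. The SAP plans counts, percentages, listings and events per 100 patient-years. It plans no between-arm ratio or test for adverse events and no dosing-day table. In the planned tables of all events, one extra day in 112 is small, and under constant rates the absolute difference does not move. Individual reactions can also be traced: SAP 10.2.3 and 10.2.5 provide for subject numbers and for listings of serious events, and Protocol 6.1 and 6.3 provide a dedicated form and blinded adjudication for suspected anaphylactic reactions. These points limit the size, and the ratio table above is only a conditional illustration. They do not correct the placebo column.

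A second argument is that the one-day gap between events and exposure is a general feature of SAP 10.2.4, since the 140-day limit produces the same gap. That is true, and the fix leaves that gap for subjects with no Period B dose. It remains the case that the formula puts the switch day's exposure in Period B.

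The third argument has the most weight. Week 16 is also the last Period A visit, with adverse event assessment and laboratory tests scheduled. An event that began or was found before the injection has the same onset date. A strict bound without onset time would move it out of the randomised comparison. The present rule, however, does not separate such events either: it places pre-dose and post-dose onsets alike in both periods. The SAP already credits dosing-day onsets to that day's dose at the start of Period A, Period B and the all-risankizumab period, and the strict bound applies the same convention at the switch.

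**Conclusion.** The concern holds. Followed exactly, SAP 10.2.1 reports a placebo subject's same-day reaction to a first risankizumab injection under placebo in Period A. This is wrong as written, not a detail left open.

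The consequence is limited. It touches one day per subject who enters Period B, the tables are descriptive, and no risankizumab event is lost, because the same event is also counted in Period B and ALL_RZB. The per-event figures (3.9 per 100 patient-years, up to 1.2% of subjects) assume that all 84 placebo subjects enter Period B on the nominal day. The pull of the dosing-day ratio towards 1 also assumes that all doses are given and that per-injection rates are constant. Without same-day rates, the number of misplaced events cannot be estimated. It should be corrected because the comparison is the only randomised one and the correction is small.

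**What to change.** In SAP 10.2.1, define a Period A event as one with onset on or after the first Period A dose date and strictly before the first Period B dose date, keeping the 140-day limit where there is no Period B dose. Assign onsets on the first Period B dose date to Period B only, which matches SAP 10.2.4. Add one exception: where onset time or a pre-/post-dose flag is available, an event documented as starting before that day's injection is counted in Period A, not Period B.

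The cost is one phrase and one sentence in the SAP, plus a pre-/post-dose flag for Week 16 onsets if event onset time is not collected. The documents do not say whether it is. SAP 9.1 requires for ePRO data that "the baseline measurement must be prior to the time of the first administration of study drug", which suggests that some dose times are available but says nothing about adverse event onset times. Without a flag, an event that began or was found at the Week 16 visit before dosing would go to Period B, which is the reverse misassignment for that event.
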